5.5. Secondary Outcomes

Table 1: All measured outcomes at different endpoints with type of data and planned statistical analyses are listed below

Outcome	Unit/options	Endpoint (days from index consultation)					Type of data	Statistical analyses
		0	0-21	7	28	60		
Secondary outcomes								
Daily total LRTI symptom score	0-36		X				Ordinal	Mean/Median, 95% CI, Chi ² or Fischer's exact
Duration of symptoms rated 3 or above	Days		X				Ratio	Mean/Median, 95% CI, Independent samples t-test/Mann Whitney U
Cancelled work related activities	Days		X				Ratio	Mean/Median, 95% CI, Independent samples t-test/Mann Whitney U
Cancelled leisure activities	Days		X				Ratio	Mean/Median, 95% CI, Independent samples t-test/Mann Whitney U
Satisfied or very satisfied (4 or 5) with index consultation	1 (very dissatisfied), 2 (dissatisfied), 3 (nor dissatisfied or satisfied), 4 (satisfied), 5 (very satisfied)	X					Nominal	Proportions, Chi ² or Fischer's exact
Type of antibiotic prescription at index consultation	Immediate/Delayed	X					Nominal	Proportion, RR, 95% CI, Chi ² or Fischer's exact
Antibiotic prescribed within 7 days after index consultation	Yes/No			X			Nominal	Proportion, RR, 95% CI, Chi ² or Fischer's exact
Antibiotic prescribed within 28 days after index consultation	Yes/No				X		Nominal	Proportion, RR, 95% CI, Chi ² or Fischer's exact
Reconsultation within 28 days after index consultation	Yes/No				X		Nominal	Proportion, RR, 95% CI, Chi ² or Fischer's exact
Hospitalization within 28 days after index consultation	Yes/No				X		Nominal	Proportion, RR, 95% CI, Chi ² or Fischer's exact
Complication within 28 days after index consultation	Yes/No				X		Nominal	Proportion, RR, 95% CI, Chi ² or Fischer's exact

Referred for suspicion of cancer (any) within 60 days after index consultation	Yes/No				X	Nominal	Proportion, RR, 95% CI, Chi ² or Fischer's exact
Diagnosed with cancer (any) within 60 days after index consultation	Yes/No				X	Nominal	Proportion, RR, 95% CI, Chi ² or Fischer's exact
All-cause mortality within 60 days after index consultation	Yes/No				X	Nominal	Proportion, RR, 95% CI, Chi ² or Fischer's exact
Adverse event within 60 days after index consultation	Yes/No				X	Nominal	Proportion, RR, 95% CI, Chi ² or Fischer's exact

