2.2. Secondary Objectives and Outcomes

Secondary objectives:

- To compare the clinical course of participants in terms of antibiotics prescribed up to day 28, duration and burden of LRTI symptoms, re-consultations, imaging performed, illness deterioration (hospitalization, complications, all-cause mortality), referral for and number of cancer diagnoses in review of medical records up to day 60, and spontaneously reported unintended events detected up to day 60.
- To assess participants' satisfaction with the index consultation.

Secondary outcomes:

1) Outcomes from the LRTI symptom diary:

Participants will be asked to complete a validated LRTI symptom diary every day from the day of index consultation (day 0) to day 21¹⁸. The recorded items include the following six symptoms of LRTI: cough, dyspnea, sputum production, well-being, sleep disturbance, and activity disturbance. The participants are asked to consider how bad each symptom has been over the past 24 hours by scoring each symptom on a 7-point Likert scale (0 = no problem, 1 = very little problem, 2 = slight problem, 3 = moderate problem, 4 = bad problem, 5 = very bad problem, and 6 = as bad as it could be). Moreover, the diary contains a social domain on cancellation of work-related or leisure activities. Only on the day of the index consultation (day 0) the diary will incorporate a question on participants' satisfaction with the consultation assessed on a 5-point Likert scale (very dissatisfied (1) to very satisfied (5)).

- 1.1) Daily total LRTI symptom score, calculated as the sum of the scores for six symptoms
(minimum 0 – maximum 36) (mean/median).
- 1.2) The number of days with symptoms rated as “moderate problem” or worse by the participant (at least one item with a score of 3 or above) (mean/median).
- 1.3) Number of days participants signed in sick/cancelled work-related activities or cancelled leisure activities (mean/median).

- 1.4) Proportion of participants who were satisfied or very satisfied (4 or 5) with the index consultation.

Outcomes 1.1, 1.2 and 1.3 from the LRTI symptom diary will be calculated for each participant every day from day 0 until the participant has scored 0 for every item, whichever comes first, or up to a maximum of 21 days.

2) Outcomes from participants' shared medication records (i.e., FMK) and on type of prescription:

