5.1. Analysis set

Analyses will be performed as intention to treat (ITT) (pragmatic trial). The primary analysis population will comprise all participants, irrespective of follow-up. We will use bootstrap to handle non-normality and use a 5% significance level.

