5.2. Lost to follow-up and missing data

In the case of missing data on the primary endpoint, the GP who enrolled the participant will be contacted to clarify if antibiotics were prescribed at the index consultation. If clarification is not obtained, we will consider it as if antibiotics were prescribed at the index consultation. We expect that the use of an e-CRF for GPs to complete at the time of index consultation will keep missing data on the primary outcome at a minimum. We expect that only observed data will be included in the secondary analyses.

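### Table 1 tests the ordered 0–36 daily symptom score with chi-square or Fisher's exact, which ignore order and test neither the mean nor the median that the row reports

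*SAP*

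**What the plan says.** SAP section 2.2 makes "duration and burden of LRTI symptoms" part of a secondary objective. Outcome 1.1 is the "Daily total LRTI symptom score, calculated as the sum of the scores for six symptoms", running from 0 to 36 and summarised by mean/median. The diary outcomes 1.1 to 1.3 are "calculated for each participant every day from day 0 until the participant has scored 0 for every item", "or up to a maximum of 21 days".

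Section 5.5, Table 1, types this score as ordinal over days 0–21. Its analysis cell reads "Mean/Median, 95% CI, Chi"-square or Fisher's exact, and names no other test. The three other diary rows with a mean/median summary (days with symptoms, cancelled work, cancelled leisure) are typed as ratio and carry "Mean/Median, 95% CI, Independent samples t-test/Mann Whitney U".

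Two general statements bear on the row. Section 5.1: "We will use bootstrap to handle non-normality and use a 5% significance level". Section 5.2: "We expect that only observed data will be included in the secondary analyses".

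**The concern.** Chi-square and Fisher's exact ask whether the two arms fill a set of unlabelled categories in the same proportions. They do not know that 20 is worse than 10. Placed beside a mean or median of a 0–36 score, they give a p-value for a different question.

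The trial tries to reduce antibiotic prescribing, so symptom burden is one of the places where a cost to patients would show. A test that is insensitive to a shift could miss a real difference in either direction, and the non-significant result could be read as reassurance. A significant result could equally arise with no difference in mean or median.

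There is a linked gap. The row covers 22 diary days (days 0 to 21), and the SAP does not say how they become one comparison.

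**Working it through.** **1. Is the score categorical anywhere in the plan?** Six items scored 0–6 give 6 × 6 = 36 as the maximum, hence 37 possible values. Neither section 2.2 (outcome 1.1) nor Table 1 gives a cut-off. Every other chi-square/Fisher row of Table 1 is typed nominal and reported as a proportion. This row alone pairs a mean/median with a test for nominal data.

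**2. Does the test use the order?** One data set was simulated with 195 per arm and the arms 2.1 points apart. The score labels were then shuffled at random.

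| | p before | p after shuffling |
|---|---|---|
| Chi-square | 0.123 | 0.123 |
| Mann-Whitney | 0.0035 | 0.154 |

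The chi-square p-value cannot change, because the statistic does not depend on the order of the columns. The same is true of Fisher's exact. This step needs no assumption about the data.

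**3. What does that cost?** The SAP gives no SD, target difference or diary completion rate for this score, so there is no plan figure to reproduce. Its only sample-size figure concerns the primary outcome: 50% versus 35%, two-sided 5%, 80% power gives 170 per arm, as section 3.3 states. The point does not depend on it.

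Assumed for illustration: one score per participant, normal with mean 14 and SD 5–7, rounded and clipped to 0–36, 150–195 diaries per arm. A 0.3 SD shift is then 0.3 × 5 = 1.5 to 0.3 × 7 = 2.1 points. With 27–33 score values observed, chi-square spreads the shift over 26–32 degrees of freedom.

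| Shift | Chi-square | Fisher's exact | Mann-Whitney / t-test |
|---|---|---|---|
| 0.3 SD | 14–23% | 17–27% | 71–86% |
| 0.5 SD | 51–71% | 55–77% | 98% or more |

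About 40–54% of expected cell counts were below 5.

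**4. Can it mislead the other way?**
- *Unequal spread.* Both means 14, SDs 5 and 7, 175 per arm: chi-square rejects in about 40% of trials, the t-test and Mann-Whitney in about 5%.
- *Daily testing.* A literal reading of a daily score gives 22 tests. With no arm difference in an assumed diary model (for example half-life 5.5 days, 175 per arm), at least one chi-square p < 0.05 occurred in roughly 45–50% of trials. As an order-of-magnitude check, 22 independent tests at chi-square's observed 3% would give 1 − 0.97^22 = 49%.

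**5. How should the days be combined?** Section 2.2 stops calculating at the first all-zero day, and section 5.2 expects observed data only. Read together, they point to recovered days dropping out. Assumed diary: day-0 mean 16, SD 6, half-life 4–7 days, 20% shorter in one arm, 175 per arm, no diary days missing before recovery.

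| Days after recovery | Mean difference | Power, Mann-Whitney / t-test |
|---|---|---|
| counted as 0 | 0.68–0.92 points | 75–81% |
| left out | 0.21–0.52 points | 15–45% |

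Zero-filling alone is not safe when diaries are incomplete. Someone who stops the diary early and unrecovered is averaged over high-score days only. With assumed stopping of 10% in one arm and 20% in the other and no true difference, a t-test on each participant's available-day mean rejected in about 32% of trials.

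**The case against.** The strongest defence is that this is a slip in one cell of a secondary outcome. The mean or median with its confidence interval is still reported, section 5.1 provides a bootstrap, and the neighbouring rows show what was probably meant. All of that stands as to weight. It does not remove the error: the bootstrap statement concerns non-normality and does not replace the test named for this row.

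It can also be said that the handling of days is an inference, and that every power figure rests on assumed inputs. Both are true. The SAP does not state that recovered days are excluded; sections 2.2 and 5.2 only point that way. The figures show direction and rough size. The order-invariance in step 2 needs no assumption.

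Three further readings are tempting and are not supported:

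- *That the fault only costs power and cannot produce a false claim.* Chi-square does reject in only about 3% of trials when a single score has the same distribution in both arms. That does not carry over to arms that differ in spread, or to 22 daily tests (step 4).
- *That the planned test has almost no power because each participant's averaged score takes so many distinct values.* The SAP never proposes to apply chi-square to an averaged score, so no such figure belongs here.
- *That copying the neighbouring cell settles the matter.* It leaves two tests open, and a Mann-Whitney p-value beside a difference in means would repeat the mismatch. The neighbouring rows are also typed ratio and this one ordinal.

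**Conclusion.** The point holds and should be fixed. The test named for the symptom score ignores the ordering of the scale and matches neither estimate in its own row. The row also leaves open how 22 days become one result.

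Under the assumed near-normal single score, a 0.3 SD difference would be detected in about 14–23% of trials by chi-square, against about 71–86% by a test of location. The same test can reject when the means are equal. These sizes depend on the assumed mean, SD, shift and number of diaries, and the daily-testing figure on an assumed diary model; none of these inputs is in the SAP.

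The consequence is limited to a secondary outcome tied to a stated objective. The primary outcome, its analysis and the sample size are unaffected.

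**What to change.** 1. In this row of Table 1, replace chi-square/Fisher's exact with one test, chosen in advance, that matches the reported estimate: the t-test with the section 5.1 bootstrap 95% CI for a difference in means, or Mann-Whitney U if a rank-based or median comparison is reported.
2. State that there is one overall comparison over days 0–21, not 22 separate tests. One suitable form is a repeated-measures mixed model of the daily scores giving the average between-arm difference over days 0–21. If that is chosen, the cell should name the model's test of that difference.
3. Add to section 2.2 that, for this comparison, days after the first all-zero score count as 0. Treat diary days missing before recovery as missing in the model, and do not average each participant over whatever days happen to be available.

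The cost is one table cell and a short rule, with no new data. The rule assumes no relapse after the first all-zero day, and the model assumes that missing diary days are missing at random. Both assumptions should be stated.

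### Participant satisfaction is compared only as 4–5 versus 1–3, and it is the one binary secondary row of Table 1 with no risk ratio and no 95% CI

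*SAP*

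**What the plan says.** SAP section 2.2 gives two secondary objectives. The second is "To assess participants' satisfaction with the index consultation", and outcome 1.4 is the only outcome that serves it. The day-0 diary records "satisfaction with the consultation assessed on a 5-point Likert scale". Outcome 1.4 then defines the result as "Proportion of participants who were satisfied or very satisfied (4 or 5) with the index consultation".

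In section 5.5, Table 1, the row "Satisfied or very satisfied (4 or 5) with index consultation" lists all five response options and types the data as nominal. Its analysis cell begins "Proportions, Chi" and plans proportions with a chi-square or Fisher test. The ten other binary rows (type of prescription, antibiotics within 7 and 28 days, reconsultation, hospitalization, complication, cancer referral, cancer diagnosis, mortality, adverse event) all begin "Proportion, RR, 95% CI" and then name the test. The primary outcome in section 5.4 also has a risk ratio and 95% CI. The SAP plans no analysis of the five levels and gives no expected distribution of satisfaction.

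**The concern.** There are two separate matters.

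- **Missing interval.** For this row alone, the plan asks for a p-value but no between-arm estimate with an interval. If the test is not significant, nothing prespecified shows which differences remain compatible with the data. The row also departs from the pattern of its own table, and that needs no assumption to see.
- **Unused information.** The cut treats satisfied and very satisfied as the same answer. If most participants are at least satisfied, much of any change would lie between those two levels, where the planned test cannot see it. A null result would then be weak evidence on the only outcome of an objective.

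**Working it through.** **The plan's own figure.** The SAP gives no power for satisfaction. Its primary sample size fixes the conventions. For 50% versus 35%, two-sided 5%, 80% power, pooled variance under the null:

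n = [1.96·√(2·0.425·0.575) + 0.8416·√(0.50·0.50 + 0.35·0.65)]² / 0.15² = (1.370 + 0.582)² / 0.0225 ≈ 169.3, so 170 per arm.

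This matches section 3.3. The same two-sided 5% level is used below.

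**Assumptions (not in the SAP).**
- 85% diary return: 0.85 × 195 ≈ 166 per arm.
- Control distribution over levels 1 to 5: A = 1/2/7/40/50% (90% at 4–5) or B = 2/4/14/45/35% (80% at 4–5).
- The effect is one common odds ratio (OR) at every boundary of the scale.

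**Worked case, A with OR 1.8.**
- 4–5 share: odds 0.90/0.10 = 9; 9 × 1.8 = 16.2; 16.2/17.2 = 0.942. The difference is 4.2 points.
- Level 5 share: odds 1; 1 × 1.8 = 1.8; 1.8/2.8 = 0.643. The difference is 14.3 points.
- Power of the cut: pooled share 0.921; null SE = √(2·0.921·0.079/166) = 0.0296; alternative SE = √((0.90·0.10 + 0.942·0.058)/166) = 0.0295; Φ[(0.0419 − 1.96·0.0296)/0.0295] = Φ(−0.55) ≈ 0.29.

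**Simulated power** (at least 20,000 trials per scenario; tie-corrected Mann-Whitney on five levels, chi-square on the cut):

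| Control | Effect | Five levels | Cut |
|---|---|---|---|
| A | OR 1.5 | 0.47 | 0.17 |
| A | OR 1.8 | 0.77 | 0.29 |
| B | OR 1.5 | 0.50 | 0.28 |
| B | OR 1.8 | 0.81 | 0.49 |
| A | OR 1/1.8 (satisfaction falls) | 0.80 | 0.44 |
| B | OR 1/1.8 (satisfaction falls) | 0.82 | 0.64 |
| A | 8 points move from 4 into 1–3 | 0.11 | 0.56 |
| B | 10 points move from 1–3 into 4 | 0.20 | 0.73 |

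In the last two rows level 5 is unchanged. With no effect, both tests reject in about 5% of trials.

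**Relative loss for improvement.** A: 1 − 0.17/0.47 = 64% and 1 − 0.29/0.77 = 62%. B: 1 − 0.28/0.50 = 44% and 1 − 0.49/0.81 = 40%.

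**Sensitivity.** With all 195 per arm and OR 1.8, five levels versus cut gives 0.83 v 0.19 when 95% of controls rate 4–5 (45% at 4, 50% at 5), 0.82 v 0.33 at 90%, 0.86 v 0.56 at 80%, and 0.90 v 0.81 at 50%. The result does not hinge on the assumed diary return. It does depend on how far ratings cluster at the top.

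**What the missing interval would show.** With 90% at 4–5 in both arms and 166 per arm, SE(log RR) = √(2·0.10/(166·0.90)) = 0.0366. The 95% CI is exp(±1.96·0.0366), or 0.93 to 1.07.

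**The case against.** The strongest defence is that the cut is the stated definition of outcome 1.4, not a slip in the analysis. For a prespecified binary outcome, proportions with chi-square or Fisher are valid. The nominal label is the one this SAP gives to every yes/no outcome, including the primary, so it is not an error in itself. The share who are at least satisfied is easy to read. In a trial meant to reduce prescribing, a rise in participants who are not satisfied may be the change of most interest, and the cut addresses that directly (the SAP states no direction). All of this stands. It is why the 4–5 proportion should not be replaced.

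Three stronger readings are tempting, and the document supports none of them.
- A reader might infer that the cut loses most of the power. That holds for improvement when about 90% or more of controls rate 4–5. At 80% the loss is roughly 40%, it is smaller again if satisfaction falls, and the cut wins when only the 3/4 boundary is crossed. The SAP does not say which case applies.
- A reader might infer that no effect can be learned from the row. Each arm's proportion is reported, so a difference could be derived. What is missing is a prespecified estimate with its interval.
- A reader might infer that a null result will be reported as no effect. That is a conjecture about the eventual report.

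The defence does not explain why this row alone lacks the risk ratio and interval, and nothing elsewhere in the SAP supplies them.

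**Conclusion.** The point holds as a minor one. The omission of a risk ratio and 95% CI is a plain inconsistency within Table 1. The loss from using only the cut is conditional: power of about 0.47–0.81 on five levels against 0.17–0.49 for the cut, assuming 166 per arm, 80–90% of controls at 4–5 and a common odds ratio of 1.5–1.8 towards higher satisfaction. Since the ranking of the two tests depends on where on the scale the effect falls, the case is for reporting both. The planned test is not invalid, and neither the primary outcome nor the sample size is affected.

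**What to change.** Leave outcome 1.4 in section 2.2 as defined. In section 5.5, Table 1:

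- add a risk ratio and 95% CI to the satisfaction row, as in the other binary rows;
- show the distribution over all five levels by arm;
- prespecify one supporting ordinal comparison: a proportional-odds model with its odds ratio and 95% CI, or Mann-Whitney with a probability-of-superiority estimate and 95% CI. Label it as supporting, so that the 4–5 proportion stays the outcome.

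The first item should be made whatever view is taken of the third. No new data are needed, and section 6 provides for revisions by version number. The change should be dated before allocation is revealed. The cost is one extra supporting comparison on a secondary outcome, and an ordinal effect measure that is less simple to read than a proportion.

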5.6 Methods for additional analyses (e.g., subgroup analyses)

We will conduct subgroup analyses of the primary outcome of participants with chronic obstructive pulmonary disease (COPD), comorbid pulmonary disease in general, with a CRP concentration > 50 mg/L or aged ≥ 80 years to determine the risk of effect modification.

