Antimicrobial resistance is one of the largest threats to global health, stated by The World Health Organization (WHO)¹. Antibiotic use is the main driver of selection of resistant bacteria², and resistance develops quickly after any antibiotic use. Primary health care is responsible for 90% of all antibiotic prescriptions in human in Denmark³. General practitioners (GPs) issue 75% of these prescriptions⁴ with acute lower respiratory tract infections (LRTIs) being one of the most common indications⁵.

Acute LRTIs includes several different conditions with overlapping symptoms such as acute bronchitis and community-acquired pneumonia (CAP)⁶. No single symptom or specific point of care test (POCT) cut-off value, e.g. C-reactive protein (CRP), can be used to discriminate the diagnoses^{7,8}. It is well known that this diagnostic uncertainty leads to overuse of antibiotics⁹.

An alternative mode of diagnosing CAP is using focused lung ultrasound FLUS. Several studies have demonstrated that FLUS has an excellent accuracy for diagnosing pneumonia in hospitalised adults¹⁰⁻¹⁵. FLUS is not a common application for GPs using point-of-care ultrasonography (POCUS)¹⁶ in general practice, even though GPs are increasingly using POCUS¹⁷. We do not know yet if FLUS can help discriminating between benign self-limiting acute LRTIs and bacterial CAP in general practice. **This trial aims to pragmatically determine if the addition of FLUS to usual care can effectively reduce the prescription of antibiotics** in patients presenting to general practice with an acute LRTI.

2. Study Objectives, Hypothesis and Outcomes

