4.2 Baseline characteristics

Patients

Date of enrolment, age, sex (provided from social security number), comorbidities, smoking status. Participants' symptoms and signs of acute LRTI, the results of physical examination and any POCT performed as part of usual care (e.g., CRP) in both groups. FLUS pathological findings will be reported for the +FLUS group.

General practitioners

Age, sex, region of Denmark, type of clinic, seniority as a GP, experience with POCUS, experience with FLUS, type of ultrasound device (hand-held, laptop or fixed), ultrasound brand and model, transducer(s) used, and baseline antibiotic prescribing.

Baseline characteristics	Unit/options	Endpoint (days from index consultation)					Type of data	Statistical analyses
		0	0-21	7	28	60		
General practitioners								

Age	Years	X				Ratio	Mean/Median, 95% CI
Sex	Male/Female	X				Nominal	Proportions
Region of Denmark	North/Central/Southern /Zealand/Capitol	X				Nominal	Proportions
Type of clinic	Solo/Partnership/ Collaboration/Other	X				Nominal	Proportions
Seniority as a GP	Years	X				Ratio	Mean/Median, 95% CI
Experience POCUS	Years	X				Ratio	Mean/Median, 95% CI
Experience FLUS	Years	X				Ratio	Mean/Median, 95% CI
Type of ultrasound machine system	Hand-held, Laptop, Stationary	X				Nominal	Proportions
Number of transducers available	Number	X				Ratio	Mean/Median, 95% CI
Type of transducer used for FLUS	Linear/curved/phased-array/other	X				Nominal	Proportions
Baseline antibiotic prescribing	Defined as daily doses per 1000 patients per year	X				Ratio	Mean/Median, 95% CI
Patients							
Date of enrolment	Date	X				Ordinal	Used to calculate age at date of enrolment
Date of birth	Date	X				Ordinal	Used to calculate age at date of enrolment
Age	Years	X				Ratio	Mean/Median, 95% CI, Independent samples t-test/Mann Whitney U
Sex	Male/Female	X				Nominal	Proportions, Chi ² or Fischer's exact
List of comorbidities	Present/not present	X				Nominal	Proportions, Chi ² or Fischer's exact
Smoking status	Smoker/former smoker/never-smoker	X				Nominal	Proportions, Chi ² or Fischer's exact
List of symptoms	Present/not present	X				Nominal	Proportions, Chi ² or Fischer's exact
List of clinical findings	Present/not present	X				Nominal	Proportions, Chi ² or Fischer's exact
List of point-of-care tests	Performed/not performed	X				Nominal	Proportions, Chi ² or Fischer's exact

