Point-of-care test results	CRP: mg/L; Leukocytes: 10 ⁹ /L; Saturation: %; Pulse: Beats/min.	X				Ratio	Mean/Median, 95% CI, Independent samples t-test/Mann Whitney U

5. Statistical Principles and Analysis

All analyses described in this plan are considered *a priori* analyses as they have been defined in the protocol or in this statistical analysis plan. If any *post-hoc* analyses are conducted, they will be defined as such in the report.

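### SAP section 5.6 examines effect modification by CRP and age through one unexplained cut each, which is inefficient because both are recorded as continuous values

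*SAP*

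**What the plan says.** Section 5.6 plans subgroup analyses of the primary outcome for four groups. Two are binary by nature: COPD ("We will conduct subgroup analyses of the primary outcome of participants with chronic obstructive pulmonary disease (COPD") and any comorbid pulmonary disease. The other two are cuts on continuous variables: "with a CRP concentration > 50 mg/L or aged ≥ 80 years to determine the risk of effect modification". The section gives no reason for 50 mg/L or 80 years, no continuous or multi-category form, and no interaction term.

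The baseline table in section 4.2 classes both variables as ratio data. CRP is listed with its unit ("CRP: mg/L; Leukocytes"). Age is in years, with dates of birth and enrolment listed as "Used to calculate age at date of enrolment". CRP is reported where it was measured: "any POCT performed as part of usual care (e.g., CRP) in both groups".

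The SAP's introduction also mentions CRP thresholds: "No single symptom or specific point of care test (POCT) cut-off value, e.g. C-reactive protein (CRP), can be used to discriminate the diagnoses".

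**The concern.** The stated purpose of section 5.6 is to determine effect modification, that is, whether the effect of FLUS on prescribing changes with CRP or with age. A single cut answers a narrower question. It treats a participant at 51 mg/L like one at 300 mg/L and unlike one at 49 mg/L, and it yields one contrast. If the effect changes gradually, the contrast discards much of the evidence for the change. If the effect peaks at intermediate CRP, on both sides of 50 mg/L, it can average out and look like no modification.

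At stake is how informative a pre-planned additional analysis can be, using values the trial already collects. The COPD and pulmonary comorbidity subgroups are not in question.

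**Working it through.** **The plan's own figure.** The SAP gives no number for the subgroup analyses. Its only size calculation is in section 3.3: 50% versus 35%, 5% significance, 80% power. With a two-sided test and pooled variance, the number per arm is [1.960·√(2 × 0.425 × 0.575) + 0.842·√(0.25 + 0.2275)]² / 0.15² = (1.370 + 0.582)² / 0.0225, or about 169.3, which rounds up to 170. The total is 340, as stated. The planned 390 (195 per arm) is used below.

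**Information kept by one cut.** Assume a normally distributed modifier (age, or log CRP) and modification linear in it. A cut with share p above it keeps φ(z)² / [p(1 − p)] of the information in the continuous term, where z = Φ⁻¹(1 − p). The SAP gives no distribution for either variable, so p is an assumption and a range is shown. The formula is symmetric, so a share of 70% above the cut gives the same result as 30%.

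| Share above cut (assumed) | z | φ(z) | Kept | Lost |
|---|---|---|---|---|
| 50% | 0 | 0.399 | 64% | 36% |
| 30% | 0.524 | 0.348 | 58% | 42% |
| 20% | 0.842 | 0.280 | 49% | 51% |
| 10% | 1.282 | 0.175 | 34% | 66% |
| 5% | 1.645 | 0.103 | 22% | 78% |

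**Size of the older subgroup.** At an assumed 5% aged 80 or over, 195 × 0.05 = 9.75 per arm. At 10%, 195 × 0.10 = 19.5 per arm.

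**Simulated power.** With N = 390, a linear-probability interaction model with robust standard errors, 4,000 runs per setting and an assumed modification of 13 percentage points per SD, the continuous term had about 77% power. The single cut had 53%, 49%, 44% and 38% with 50%, 30%, 20% and 10% above it.

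**Smaller modification.** Thirteen points per SD is close to the whole 15-point planned effect. Power of 77% on 1 df corresponds to a noncentrality of (1.960 + 0.739)² ≈ 7.28. Scaling it by (7.5/13)² gives 2.42, and by (5/13)² gives 1.08. Multiplying by the kept share gives the cut:

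| Modification per SD (assumed) | Linear, 1 df | Curve, 2 df | Cut, 50% above | Cut, 30% | Cut, 20% | Cut, 10% | Cut, 5% |
|---|---|---|---|---|---|---|---|
| 13 points | 77% | 67% | 58% | 53% | 47% | 35% | 25% |
| 7.5 points | 34% | 27% | 24% | 22% | 19% | 15% | 11% |
| 5 points | 18% | 14% | 13% | 12% | 11% | 9% | 8% |

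The first row differs from the simulation by a few points because it is a large-sample approximation. A 3-df curve at 13 points per SD has 61%.

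**If the effect really steps at the cut.** The cut then loses nothing, but power is still low. With average variance (0.25 + 0.2275)/2 = 0.23875, the standard error of the difference between two subgroup risk differences is √[2 × 0.23875/(195p) + 2 × 0.23875/(195(1 − p))]. This is 0.099 at p = 50%, 0.124 at 20%, 0.165 at 10% and 0.227 at 5%. Power to detect a 15-point difference is about 33%, 23%, 15% and 10%.

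**The case against.** **A contradiction with the introduction.** A reader might infer that the SAP refutes itself by rejecting CRP cut-offs and then using one. The text does not support this. The introduction is about telling diagnoses apart; section 5.6 defines a subgroup and makes no diagnostic claim. A value that cannot diagnose pneumonia may still mark a group of interest. The cuts are also fixed in advance rather than chosen from the data.

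**An off-centre CRP cut.** A reader might also infer that 50 mg/L lies far from the middle of the distribution. The SAP gives no CRP distribution, and section 4.1 enrols only patients in whom the GP suspects pneumonia, so a share near one half is not excluded. For CRP the loss could be the minimum of 36%.

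**A curve does not recover the quoted loss.** The retention figures compare a cut with a 1-df linear term. Under a linear trend, a quadratic or spline test spends extra degrees of freedom, and its advantage over a median cut shrinks to 67% (2 df) or 61% (3 df) against 58%. Nor do these figures measure the risk of missing a peak at intermediate CRP, and nothing in the SAP says that a scan matters most there. This objection stands and shapes the fix.

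**Limited consequence.** CRP is available only where usual care included it, which limits any approach. Interaction power is low under most assumptions. The primary estimate and the sample size are untouched. All of this stands.

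What the objections leave in place is that a linear continuous term uses collected data better than one unexplained cut whenever the effect changes roughly linearly.

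**Conclusion.** The point holds as a question of efficiency in a secondary analysis, not as an error or inconsistency. Section 5.6 reduces two ratio-scale variables to one cut each without giving a reason. Under linear modification on a normal scale, at least 36% of the information is lost, and about half or more if 20% or fewer lie above the cut. The age cut is the likelier to be costly, on the assumption that few participants are 80 or over. For CRP the size of the loss cannot be fixed from the SAP.

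The result rests on assumed shares and an assumed linear trend. A true step at 50 mg/L or 80 years would reverse it, though the SAP gives no reason to expect one. The weight is minor: a cheap improvement that leaves the primary result as it is.

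**What to change.** In section 5.6, pre-specify treatment-by-age and treatment-by-log-CRP interaction terms on the continuous scale, each tested with a 1-df linear term. For CRP, restrict the analysis to participants with a result and report how many that is per arm. Add a quadratic or spline curve of the effect against CRP as a descriptive check of shape, not as the test, because the extra degrees of freedom cost power. Keep CRP > 50 mg/L and age ≥ 80 years as descriptive subgroup displays, with a sentence on why those values were chosen. COPD and pulmonary comorbidity stay as planned.

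The cost is SAP wording, handled through the versioned revisions that section 6 provides for, and a little extra analysis; no new data are needed. Writing it in now also keeps a later continuous analysis from being classed as post hoc under section 5. The downsides are a slightly harder presentation and a linearity assumption in the test. The change does not make the trial well powered for interaction, and the report should say so.
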